16.1 Study Leadership and Governance

16.1.1 Steering Committee

The Steering Committee will include members of the executive committee, representatives from NIH, representatives from the advisory groups/ cores and the PI from each of the collaborating health care systems. The steering committee will provide direct oversight of ICD-Pieces and set policies and procedures for the study. The steering committee will be the first resource both for planning and implementing strategies and also for receiving information from the study sites. The steering committee will review all study outcomes. During the implementation phase, the steering committee will hold monthly telephone conferences and a face-to-face meeting in Dallas, TX at the beginning of the implementation period and yearly thereafter till the end of the study. PIs at each HCS are [name] at PHHS, [name] at THR, [name] in ProHealth Physicians, and [name] and [name] at VA North Texas Healthcare Systems.

16.1.3 Conflict of Interest Policy

The UT Southwestern Office of Research Compliance conflict of interest policy is in compliance with the PHS regulation (42 C.F.R. Part 50, Subpart F).

Appendix I: CHRONIC KIDNEY DISEASE (CKD) HYPERTENSION MANAGEMENT PROTOCOL

This protocol will be initiated as directed by CHRONIC KIDNEY DISEASE (CKD) CHRONIC DISEASE MANAGEMENT PROTOCOL.

Protocol will be reviewed every year.

RN will perform protocol with assistance from PA or NP at same clinical site.

PA or NP may suggest deviations from protocol as deemed clinically appropriate.

Orders (except medication orders) will be placed by RN in electronic medical record using "per protocol" order mode with physician, PA or NP as authorizing provider. Medication orders may be routed to provider as suggested per protocol, but medication and dose will ultimately be selected and ordered by provider. After medication orders are finalized by provider, RN will notify patient of final decision.

Goals/Background

1. Chronic Kidney Disease (CKD) is defined as (for the purposes of this protocol):
 - a. Glomerular Filtration Rate (GFR) < 60 mL/min
 - b. Or presence of proteinuria, defined as any one of the following:
 - i. Random Urine Protein/Creatinine Ratio > 200 mg/g
 - ii. Random Urine Microalbumin/Creatinine Ratio > 30 mg/g
 - iii. 24 hour Urine Protein > 150mg
 - iv. Urine dipstick protein (adjusted for specific gravity)
2. Blood pressure (BP) goals
 - a. For patients with CKD goal blood pressure is Systolic (SBP) < 140 mmHg AND Diastolic (DBP) < 90 mmHg
3. ACEi/ARB
 - a. All patients with chronic kidney disease (with or without proteinuria) should be treated with an angiotensin converting enzyme inhibitor (ACEi) or angiotensin receptor blocker (ARB).
 - b. Recommended ACEi: lisinopril
 - i. Starting dose 5mg once daily if GFR > 10 mL/min or 2.5mg if GFR < 10mL/min
 - ii. Maximum dose 40mg once daily
 - iii. Class-specific considerations. Be aware of these potential adverse effects when conduction follow-up of initiation or titration of this medication (details on the follow-up process are below).
 1. Elevated potassium (hyperkalemia)
 2. Reduction in kidney function (increase in creatinine or decrease in GFR)
 3. Dry cough

- 4. Facial swelling (angioedema)
- c. Recommended ARB: losartan
 - i. Starting dose 25mg once daily
 - ii. Maximum dose 100mg once daily
 - iii. Class-specific considerations. Be aware of these potential adverse effects when conduction follow-up of initiation or titration of this medication (details on the follow-up process are below).
 - 1. Hyperkalemia
 - 2. Reduction in kidney function (increase in creatinine or decrease in glomerular filtration rate)
 - 3. Very rarely causes dry cough
 - 4. Facial swelling (angioedema)

RN BP ASSESSMENT

- 1. RN BP Assessment Visit
 - a. Pre-Visit Planning: perform 1-2 weeks prior to appointment.
 - i. Call patient
 - 1. Request patient bring all pill bottles to appointment.
 - 2. If patient has home blood pressure device, ask patient to bring home device and written home blood pressure log (after checking blood pressure twice daily for 1 week) to appointment.
 - ii. GFR Assessment
 - 1. Review prior labs in "Results Review".
 - 2. Review last potassium, creatinine and glomerular filtration rate (GFR) in last 6 months.
 - 3. If all present within 6 months, no further action needed for GFR assessment.
 - 4. If no creatinine and GFR in last 6 months, order "CREATININE with-GFR".
 - 5. If no potassium in last 6 months, "POTASSIUM LEVEL".
 - 6. Compare most recent GFR with second most recent GFR. If most recent GFR is > 20% lower, discuss with provider.
 - 7. If GFR < 60 but >/= 30, update problem list to include "CKD Stage 3"
 - 8. If GFR < 30 but >15, update problem list to include "CKD Stage 4".
 - 9. If GFR < 15, update problem list to include "CKD Stage 5"
 - iii. Proteinuria Assessment
 - 1. Review prior urine protein testing in "Results Review" for following results in last 1 year:
 - a. Microalbumin/Creatinine Ratio, Urine, Random
 - b. Protein, Urine and Creatinine, Urine (both are required as ratio must be calculated manually by dividing urine

- protein by urine creatinine).
- c. Protein, 24 hour, Urine
- d. Urine dipstick protein (adjusted for specific gravity)
- 2. If labs are present in last year, no further action is needed for Proteinuria Assessment.
- 3. If none are available, order MICROALBUMIN/CREATININE RATIO

NOTE: "Unable to calculate" for Microalbumin/Creatinine Ratio implies zero protein present in urine.

- b. Assessment of BP goal
Goal blood pressure is SBP < 140 mmHg AND DBP < 90 mmHg.
- c. Provide education annually on non-pharmacologic management of hypertension.
 - i. Low Sodium Diet
 - 1. Discuss with patient importance of low sodium diet included no added salt as well as checking labels for processed foods.
 - 2. Provide patient with Exit Care SmartText in Patient Instructions: DIET-2 GRAM LOW SODIUM (choose appropriate language).
 - 3. Refer to nutrition at same clinical site for further counseling as needed.
 - ii. Avoidance of daily use of non-steroidal anti-inflammatory drugs (NSAIDs).
 - 1. Discuss with patient that NSAIDs (included ibuprofen and naproxen) can increase blood pressure as well as cause further kidney damage.
 - 2. Discuss with provider as needed to identify alternatives to daily NSAIDs.
 - iii. Moderation of alcohol (less than 2 servings per day).
 - 1. Discuss with patient that daily alcohol consumption can raise blood pressure.
 - 2. If needed, provide patient with Exit Care SmartText in Patient Instructions: ALCOHOL AND DRUG ABUSE (choose appropriate language).
 - 3. Refer for substance abuse counseling as needed.
 - iv. Importance of exercise > 3 days per week.
 - 1. Discuss with patient that regular exercise can lower blood pressure.
 - 2. Provide patient with Exit Care SmartText in Patient Instructions: PKAMB OPC EXERCISE TO LOSE WEIGHT
 - v. Abstinence from nicotine products.
 - 1. Discuss with patient that all nicotine products can raise blood pressure.
 - 2. If active smoker, perform 'Ready to Quit' assessment in social history section Epic and refer to Smoking Cessation Clinic if

patient is ready to quit.

3. Provide patient with Exit Care SmartText in Patient Instructions: SMOKING CESSATION (choose appropriate language).

vi. Maintenance of optimal weight is body mass index (BMI) 20.0 to 25.0.

1. Discuss with patient that maintenance of normal BMI can improve blood pressure.
2. If BMI > 25.0
 - (a) Provide patient with both of following Exit Care SmartText in Patient Instructions: DIET—CALORIE COUNTING (choose appropriate language) and DIET— LOW-FAT, LOW-SATURATEDFAT, LOW-CHOLESTEROL DIETS (choose appropriate language)
3. Refer to nutrition at same clinical site as needed for dietary counseling.

vii. Avoidance of daily use of over-the-counter decongestants (pseudoephedrine or phenylephrine).

1. Discuss with patient that prolonged use of decongestants can raise blood pressure.
2. Discuss with provider as needed for alternatives to decongestants for control of symptoms.

viii. RN Blood Pressure Assessment: Ask patient about missed doses of BP medications in last 24 hours. If any missed doses, reschedule BP measurement 1-2 weeks after improved adherence. Ask patient about use of nicotine products. Wait 30 minutes after last use before measuring blood pressure. Measure and record blood pressure according to JNC 8 standards: After patient has sat quietly for 5 minutes in chair, measure with arm supported at heart level and with legs uncrossed and feet on the floor. Obtain at least two measurements and record the average of the two —sum of systolic values divided by 2 and sum of diastolic values divided by 2. (See Page number 4 (which is page 20 of 52 including introductory section) of the following link for full details:
<http://www.nhibi.nih.gov/guidelines/hypertension/express.bdf>).

1. "RN BP measurement" below refers to average calculated as above per JNC 8 guidelines.
2. If patient does not have written home blood pressure log and RN BP measurement is > 140 mmHg systolic or > 90 mmHg diastolic, initiate CKD HYPERTENSION PROTOCOL and perform at this visit.
3. If patient does not have written home blood pressure log, and RN BP measurement systolic < 140 mmHg AND diastolic < 90 mmHg, no further action is necessary.
4. Home Blood Pressure Device Validation
 - a If patient provides written home blood pressure log, review documentation in overview section of CKD diagnosis in problem list for date of last blood pressure device validation.

- i. If validation in < 1 year, proceed to "Home Blood Pressure Log Review".
- ii. If no validation in > 1 year and patient did not bring home blood pressure device, then schedule follow-up appointment in 1-2 weeks with RN. Ask patient to provide new written blood pressure log and bring home blood pressure device to appointment for comparison with RN measurement.
- iii. If no validation in > 1 year and patient brings home blood pressure device, obtain measurement from home blood pressure device.
 - 1. Ask patient to demonstrate proper use of device and provide education as needed according to JNC 8 guidelines above.
 - 2. If difference > 10 mmHg (systolic or diastolic) between home device and RN measurement, disregard home blood pressure log and notify patient that device is not sufficiently accurate. a. Under CKD diagnosis in Problem List, record in Overview section: "Home BP Device Validation [DATE]: home device not consistent with RN measurement."
 - 3. If difference < 10 mmHg (systolic or diastolic), under CKD diagnosis in Problem List, record in Overview section: "Home BP Device Validation [DATE]: home device validated as consistent with RN measurement" and proceed to "Home Blood Pressure Log Review".

5. Home Blood Pressure Log Review

- a If BP cuff is validated as above and home BP log is used in clinical decision-making, log should be scanned into Epic.
- b Calculate average of seven most recent systolic and diastolic values (i.e. sum of seven most recent systolic values divided by 7; and sum of seven most recent diastolic values divided by 7).
- c If average systolic > 140 mmHg or average diastolic > 90 mmHg, initiate CKD HYPERTENSION PROTOCOL and perform at this visit.
- d If average systolic < 140 mmHg AND average diastolic < 90 mmHg, no further action is necessary.
- e Consider extenuating circumstances such as acute pain and acute psychological distress. Discuss with provider if you feel such extenuating circumstances are contributing to blood pressure elevation. Consider rescheduling RN BP Assessment Visit in 2-4 weeks to reassess.

- f Assess for adverse effects every visit including class-specific considerations above as well as side effects common to many blood pressure medications which include (but are not limited to) lightheadedness and fainting.
 - (i) If any new adverse effects, discuss with provider.
 - (ii) If no new adverse effects, proceed to BP Medication Adherence Assessment.
- g BP Medication Adherence Assessment
 - (i) Ask patient about each BP medication and ask, "How many days per week do you forget your [insert BP medication]?"
 - (ii) If one day or less, consider adherent by self-report.
 - (iii) Review BP medication bottles if available.
 - (iv) If medications are filled at Parkland pharmacy, review refill history in Cerner for last 6 months. Consider adherent if obtains within 6 days for a 30 day prescription or within 18 days for a 90 day prescription.
 - (v) If not adherent by self-report or refill history, discuss with patient importance of adherence.
 - (a.) Reschedule RN BP Assessment Visit in 2 weeks after improved adherence.
 - (b.) If patient was deemed non-adherent on two consecutive visits, refer to clinical pharmacist for medication review and assistance with barriers to adherence (cost, complexity, etc).
 - (vi) If considered adherent by self-report and refill history, proceed to "Medication Adjustment".

6. Medication Adjustment

- a If patient is already on ACEi or ARB but not at maximum tolerated dose (see above), increase dose to achieve SBP and DBP goal (as per ACEi/ARB PROTOCOL below)
- b If patient is on maximum tolerated dose of ACEi or ARB, proceed to NON ACEi/ARB PROTOCOL.
- c If patient is not on ACEi or ARB, confirm allergies with patient.
- d If no prior allergy or adverse reaction to ACEi or ARB, proceed to ACEi/ARB PROTOCOL.
- e If prior allergy to ACEi is cough, proceed to ACEi/ARB PROTOCOL.
- f If prior allergy or adverse reaction to ACEi or ARB other than cough, consult with provider safety of starting ACEi or ARB.
- g If after discussion with provider, ACEi and ARB are both considered contraindicated, update allergies as needed

and proceed to NON-ACEi/ARB PROTOCOL.

ACEi/ARB PROTOCOL

1. Consider this protocol active until completed.
2. Review "Results Review" for past potassium and creatinine (abbreviated as "Cr" and "K" respectively hereafter). If both are available, no further action is needed. If one or both is not available in last 3 months, order both CREATININE LEVEL and POTASSIUM LEVEL as appropriate (referred to as "Cr/K Check" hereafter).
 - a. Lab Results Interpretation
 - i. Is K > 4.9?
 1. Yes
 - a. Discuss with provider before starting or increasing ACEi or ARB.
 2. No
 - a. If not on ACEi/ARB, and no prior allergy to ACEi or ARB, route pended order to provider for lisinopril 5mg once daily and proceed to "Follow-Up" below.
 - b. If not on ACEi or ARB and prior cough due to ACEi but no other ACEi or ARB allergy, route pended order to provider for losartan 25mg once daily and proceed to "Follow-Up" below.
 - c. If already on ACEi or ARB, but not at maximum tolerated dose, increase dose and proceed to "Follow-Up" below.
 - d. If already on ACEi/ARB at maximum tolerated dose, consider this protocol COMPLETED and proceed to NON-ACEi/ARB PROTOCOL.
 - e. Follow-Up
 - f. Schedule RN BP Assessment Visit and Cr/K Check 1-3 weeks following initiation or dose increase. Request patient to have labs drawn prior to appointment.
 - b. K Interpretation
 - i. Is K > 5.4?
 1. Yes. Discuss with provider stopping ACEi/ARB
 2. No
 - ii. 1. Is K > 4.9?
 3. Yes
 - a. Continue ACEi/ARB at current dose.
 - b. Provide patient with low potassium diet handout
 - c. Order repeat POTASSIUM LEVEL in 1 week.
 - d. If K is not < 5.0 on repeat evaluation, discuss with provider.
 - e. If K is </= 4.9, proceed to Cr Interpretation.
 4. No - proceed to Cr Interpretation.

- c. Serum Creatinine (Cr) Interpretation
 - ii. Is Cr >20% higher than value prior to initiation or last increase of ACEi/ARB?
 - 1. Yes. Discuss with provider decreasing dose by 50% (or stopping if at starting dose). Discuss follow up plan for Cr with provider as well.
 - 2. No
 - (i) Is creatinine within 30% of baseline since initiation?
 - (a) No. Discuss with provider decreasing dose by 50% (or stopping if at starting dose). Discuss follow up plan for Cr with provider as well.
 - (b) Yes. Proceed to RN BP Assessment.
 - 3. RN BP Assessment
 - a. Perform RN BP Assessment as detailed above.
 - b. Is BP at goal based on definitions above?
 - i. Yes. Continue regimen and schedule RN BP Assessment Visit in 3 months and follow-up with PCP within 6 months.
 - 1. If BP continues to be at goal in 3 months, this protocol is COMPLETE and can return hypertension management to PCP.
 - ii. No
 - 2. Is ACEi/ARB at maximum tolerated dose?
 - (i) Yes. This protocol is COMPLETE. Initiate NON-ACEi/ARB PROTOCOL.
 - (ii) No route pended order to provider for double prior dose of current ACE and return to "Follow-Up" above.

NON ACEi/ARB PROTOCOL

- 1. Discuss with provider selection of next anti-hypertensive protocol.
- 2. Discuss following medication suggestions with provider. These are only suggestions to guide management, but final selection is at provider's discretion.
 - a. If patient has history of myocardial infarction or heart failure, recommend BETA-BLOCKER PROTOCOL.
 - i. Recommend carvedilol given dual properties of heart rate reduction (beta blockade) and vasodilation (alpha blockade) and, therefore, typically greater impact on blood pressure.
 - ii. Recommended starting dose: carvedilol 6.25mg twice daily.
 - iii. Maximum dose: carvedilol 25mg twice daily.
 - iv. Class-specific considerations
 - 1. Low heart rate (bradycardia)
 - 2. Lower extremity swelling, erectile dysfunction, fatigue.
 - 3. Exacerbation of asthma or chronic obstructive lung disease symptoms (shortness of breath or wheezing).
 - b. If patient is on maximum tolerated beta-blocker or has no history of myocardial infarction or heart failure, recommend DIURETIC PROTOCOL.
 - i. For patients with GFR > 30 mL/min, recommend chlorthalidone.
 - 1. Starting dose 12.5mg once daily.
 - 2. Maximum dose 25mg once daily. However, dose adjustment is dependent on provider assessment of volume status. All follow-up

evaluations should be discussed with provider.

- ii. For patients with GFR < 30, recommend furosemide.
 - 1. Starting dose 20mg twice daily.
 - a. Maximum dose dependent on provider assessment of volume status. All follow-up evaluations should be discussed with provider.
- iii. Class-specific considerations
 - 1. Must counsel patients that diuretics will increase urinary frequency
 - 2. May worsen prostate symptoms in men.
- c. If patient is already on maximum tolerated diuretic and no history of myocardial infarction or heart failure, recommend CALCIUM CHANNEL BLOCKER PROTOCOL.
 - i. For patients with proteinuria, recommend non-dihydropyridine calcium channel blocker (CCB) verapamil SR as it may help reduce proteinuria.
 - 1. Recommended starting dose verapamil SR 120mg once daily.
 - 2. Maximum dose verapamil SR 360mg once daily.
 - ii. For patients without proteinuria, dihydropyridine CCB amlodipine may be used.
 - 1. Recommended starting dose amlodipine 5mg once daily.
 - 2. Maximum dose amlodipine 10mg once daily.
 - iii. Class-specific considerations
 - 1. Amlodipine may cause increased heart rate (reflex tachycardia).
 - 2. Verapamil may cause bradycardia and constipation.

Both may cause lower extremity swelling.
- d. If patient is already on maximum tolerated doses of beta-blocker, diuretic and calcium channel blocker, recommend HYDRALAZINE PROTOCOL.
 - i. Hydralazine
 - 1. Recommended starting dose 10mg three times daily.
 - 2. Maximum dose 100mg three times daily.
 - iii. Class-specific considerations
 - 1. May cause reflex tachycardia.
- e. If patient is already on maximum tolerated doses of beta-blocker, diuretic and calcium channel blocker and hydralazine, discuss with provider the following:
 - i. Referral to Hypertension Clinic.
 - ii. Referral to clinical pharmacist for full medication review and assessment of adherence.
 - iii. Return management of hypertension to PCP for work-up of secondary hypertension and selection of fifth anti-hypertensive agent.

BETA-BLOCKER PROTOCOL

1. Discuss following medication suggestions with provider. These are only suggestions to guide management, but final selection is at provider's discretion.
2. Perform RN BP Assessment as detailed above.
3. Is BP at goal?
 - a. Yes. Continue regimen and schedule RN BP Assessment Visit in 3 months and follow-up with PCP within 6 months.
 - i. If BP continues to be at goal in 3 months, can return hypertension management to PCP.

- b. No 4 is HR > 60?
 - i. Yes. Route pended order to provider for carvedilol 6.25mg twice daily (or alternative beta-blocker as directed by provider) and schedule for "Follow-Up" as detailed below in 2-4 weeks.
 - ii. No. Discuss with provider safety of starting beta-blocker or alternatively selection of diuretic, calcium channel blocker or hydralazine protocols.
- 4. Follow-Up
 - a. Perform RN BP Assessment as detailed above in 2-4 weeks.
 - b. Is BP at goal?
 - i. Yes. Continue regimen and schedule RN **BP** Assessment Visit in 3 months and follow-up with PCP within 6 months.
 - 1. If BP continues to be at goal in 3 months, can return hypertension management to PCP.
 - ii. No. Is HR > 60?
 - 1. Yes. Is beta-blocker at maximum dose?
 - a. No. Route pended order to provider for double prior dose of beta-blocker and schedule for "Follow-Up" as detailed above in 2-4 weeks.
 - b. Yes. Return to NON-ACEi/ARB PROTOCOL for selection of next medication.
 - 2. No. Discuss with provider safety of continuing beta-blocker or selection of diuretic, calcium channel blocker or hydralazine protocols.

DIURETIC PROTOCOL

- 1. Discuss following medication suggestions with provider. These are only suggestions to guide management, but final selection is at provider's discretion.
- 2. Perform RN BP Assessment as detailed above.
- 3. Is BP at goal?
 - a. Yes. Continue regimen and schedule RN BP Assessment Visit in 3 months and follow-up with PCP within 6 months.
 - i. If BP continues to be at goal in 3 months, can return hypertension management to PCP.
 - b. No. Proceed with diuretic selection
- 4. Diuretic selection
 - a. If no K or GFR in last three months then order POTASSIUM LEVEL and CREATININE WITH eGFR in EHR.
 - i. Is K > 3.5?
 - 1. No. Discuss with provider safety of initiation or titration of diuretic or need for potassium supplementation and schedule for "Follow-Up" as detailed below in 2-4 weeks after provider has provided recommendation.
 - 2. Yes. Is patient already taking diuretic?
 - a. Yes. Discuss with provider next choice (consider recommendations below based on GFR) and schedule for "Follow-Up" as detailed below in 2-4 weeks.

- b. No. Is GFR > 30?
 - (i) Yes. Recommend thiazide diuretic such as chlorthalidone 12.5mg or other diuretic selected by provider and schedule for "Follow-Up" as detailed below in 2-4 weeks.
 - (ii) No. Recommend furosemide 20mg twice daily or other diuretic selected by provider and schedule for "Follow-Up" as detailed below in 2-4 weeks.

5. Follow-Up

- a. Schedule RN BP Assessment Visit in 2-4 weeks
- b. Order POTASSIUM LEVEL and CREATININE WITH E-GFR and request patient have labs drawn at least 1 business day prior to visit.
- c. Perform RN BP Assessment as detailed above in 2-4 weeks.
- d. Is K > 3.4?
 - i. No. Discuss with provider change in therapy or potassium supplementation. Discuss follow up plan for K with provider as well.
 - ii. Yes
 - 1. Is GFR > 10% lower than last value?
 - a Yes. Discuss with provider decrease in diuretic dose or stopping diuretic. Discuss follow up plan for Cr with provider as well.
 - b No. Is BP at goal?
 - (i) If BP is still not at goal at maximum tolerated dose of diuretic, return to NON-ACEi/ARB PROTOCOL.
 - (ii) If BP is still not at goal and not taking chlorthalidone 25mg or maximum tolerated dose of diuretic, then discuss with provider if dose of diuretic should be increased.
 - (iii) If provider recommends to increase dose, schedule for "Follow-Up" as detailed above in 2-4 weeks.
 - (iv) If provider recommends to not increase dose, return to NON-ACEi/ARB PROTOCOL.

CALCIUM CHANNEL BLOCKER PROTOCOL

1. Discuss following medication suggestions with provider. These are only suggestions to guide management, but final selection is at provider's discretion.
2. Perform RN BP Assessment as detailed above.
3. Is BP at goal?
 - a. Yes. Continue regimen and schedule RN BP Assessment Visit in 3 months and follow-up with PCP within 6 months.
 - i. If BP continues to be at goal in 3 months, can return hypertension management to PCP.
 - b. No. Is patient already taking calcium channel blocker (CCB)?
 - i. Yes - Is CCB at maximum dose?
 - 1 Yes. Return to NON-ACEi/ARB PROTOCOL.
 - 2 No. Route pended order to provider for double dose of current CCB and schedule for "Follow-Up" as detailed below in 2-4 weeks.
 - a No. Does patient have proteinuria as defined above?
 - b Yes. Route pended order for verapamil SR 120mg once daily and

proceed to "Follow-Up" below.

c No. Route pended order for amlodipine 5mg once daily and schedule for "Follow-Up" as detailed below in 2-4 weeks.

4. Follow-Up

- Perform RN BP Assessment as detailed above in 2-4 weeks.
- Is HR ≥ 100 ?
 - Yes - discuss with provider
 - No. Is BP at goal?
 - Yes. Continue regimen and schedule RN BP Assessment Visit in 3 months and follow-up with PCP within 6 months.
 - If BP continues to be at goal in 3 months, can return hypertension management to PCP.
 - No. Is CCB at maximum dose?
 - No. Route pended order to provider for double dose of current CCB and return to follow-up above.
 - Yes. Return to NON-ACE i/ARB PROTOCOL.

HYDRALAZINE PROTOCOL

- Discuss following medication suggestions with provider. These are only suggestions to guide management, but final selection is at provider's discretion.
- Perform RN BP Assessment as detailed above.
- Is BP at goal?
 - Yes. Continue regimen and schedule RN BP Assessment Visit in 3 months and follow-up with PCP within 6 months.
 - If BP continues to be at goal in 3 months, can return hypertension management to PCP.
 - No. Route pended order to provider for hydralazine 10mg PO TID. If patient is already taking hydralazine 10mg PO TID, route pended order to provider for dose to 25mg PO TID. If patient is already taking 25mg or more TID, route pended order to provider for double current dose of hydralazine if not at maximum dose. Schedule for "Follow-Up" as detailed below in 2-4 weeks.
- Follow-Up
 - Perform RN BP Assessment as detailed above in 2-4 weeks.
 - is HR > 100 ?
 - Yes. Discuss with provider
 - No. Is BP at goal?
 - Yes. Continue regimen and schedule RN BP Assessment Visit in 3 months and follow-up with PCP within 6 months.
 - If BP continues to be at goal in 3 months, can return hypertension management to PCP.
 - No. Is hydralazine at maximum dose?
 - No. Route pended order to provider for double current dose of hydralazine and return to follow-up above.
 - Yes. Return to NON-ACEi/ARB PROTOCOL.

References

James PA et al. 2014 Evidence-based Guideline for the Management of High Blood Pressure in Adults. Report from the Panel Members Appointed to the Eighth Joint National Committee (JNC 8). *JAMA* 2014, 311(5):507-520

Kidney Disease: Improving Global Outcomes (KDIGO) CKD Work Group. KDIGO 2012 Clinical Practice Guideline for the Evaluation and Management of Chronic Kidney Disease. *Kidney International* 2013, Supp 3:1-150

Kidney Disease: Improving Global Outcomes (KDIGO) Blood Pressure Work Group. KDIGO Clinical Practice Guideline for the Management of Blood Pressure in Chronic Kidney Disease. *Kidney International* 2012, Supp 2:337-414

K/DOQI Clinical Practice Guidelines for Chronic Kidney Disease: Evaluation, Classification and Stratification. *Am J Kidney Dis* 2002, 39: S266.

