7.3 Follow up Visits

Measures of blood pressure, blood glucose, kidney function (creatinine, eGFR), lipid levels, urine protein/urine albumin as well as pre-specified safety events will be captured from electronic health records at the time of patient contacts with the healthcare system for scheduled or unexpected visits for patients. Information will be then directed to primary care teams per study protocol.

Main study outcomes will be captured throughout the study for both intervention and control groups using the same tools in the electronic health record and access to DFW Regional Hospital Council, ProHealth database and VA electronic information systems.

The study does not specify the frequency of visits for study participants. It is anticipated that patients with the triad of CKD, diabetes and hypertension will usually be seen at a minimum of every 3-6months in most participating clinics.

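### Appendix I validates a home blood pressure monitor when only one component agrees with the nurse's reading, so a 15/5 mmHg difference meets both the reject and the validate rule

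*Combined protocol and SAP*

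**What the plan says.** The rules are in Appendix I (CKD hypertension management protocol), under Home Blood Pressure Device Validation, item 4.a.iii. They apply when a patient brings a home monitor that has not been validated within the past year.

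- Step 2, reject: "If difference > 10 mmHg (systolic or diastolic) between home device and RN measurement, disregard home blood pressure log and notify patient". The nurse also charts the device as inconsistent with the nurse's measurement.
- Step 3, validate: "If difference < 10 mmHg (systolic or diastolic), under CKD diagnosis in Problem List, record in Overview section". The entry states that the device agrees with the nurse's measurement, and the nurse goes on to the Home Blood Pressure Log Review.

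In that review, item 5d reads: "If average systolic < 140 mmHg AND average diastolic < 90 mmHg, no further action is necessary". Item 5c starts the hypertension protocol if either average is above its limit.

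Elsewhere the appendix joins the two components with AND when a rule requires pressure to be below a limit. The target is "Goal blood pressure is SBP < 140 mmHg AND DBP < 90 mmHg", and the rule for patients without a home log is "RN BP measurement systolic < 140 mmHg AND diastolic < 90 mmHg, no further action is necessary".

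**The concern.** The opposite of 'systolic or diastolic differs by more than 10' is 'neither differs by more than 10'. Step 3 changes the direction of the inequality but keeps the 'or', so the two rules are not complements. A device that is well off on one component and close on the other qualifies for two contradictory chart entries and two opposite uses of its log.

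Two features of the appendix give the slip some weight:

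- **The validated entry persists.** Under item 4.a.i, a validation less than a year old sends the log straight to review. Participation lasts 12 months (Section 4), so one wrong entry could cover most or all of a patient's follow-up.
- **The log displaces the nurse's reading.** Items 2 and 3 of the nurse assessment act on the nurse's reading only when there is no written home log. Once a log is accepted, items 5c and 5d act on the log average.

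A blood pressure below 140/90 mmHg is a named intervention target in Section 6.5, which refers to the appendices for the detailed protocols.

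**Working it through.** No figure in the plan bears on this, so the check is a truth table. Let S and D be the absolute systolic and diastolic differences between device and nurse, in mmHg.

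- Reject (step 2): S > 10 or D > 10.
- Validate as written (step 3): S < 10 or D < 10.
- Alternative A: S < 10 and D < 10.
- Alternative B: S ≤ 10 and D ≤ 10.

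Each component can be below, at or above 10, represented here by 5, 10 and 15. The last three columns show the outcome when step 2 is combined with each version of step 3.

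| S/D | Step 3 as written | Alternative A | Alternative B |
|---|---|---|---|
| 5/5 | validate | validate | validate |
| 10/5, 5/10 | validate | **neither** | validate |
| 10/10 | **neither** | **neither** | validate |
| 15/10, 10/15, 15/15 | reject | reject | reject |
| 15/5, 5/15 | **both** | reject | reject |

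The same check over all whole-number differences from 0 to 30 mmHg (31 × 31 = 961 pairs) gives:

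- As written: both rules are met in 2 × 20 × 10 = 400 pairs (one component 11 to 30, the other 0 to 9). Neither is met in 1 pair (10/10).
- Alternative A: both in 0 pairs; neither in 10 + 10 + 1 = 21 pairs, those with one component at exactly 10 and the other at 10 or less.
- Alternative B: both in 0 pairs; neither in 0 pairs.

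These counts describe the logic only. They do not estimate how often patients fall in the overlap.

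A constructed example shows the consequence. The nurse reads 150/85, the device reads 135/80, and the log averages 135/80.

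1. 150 − 135 = 15 > 10, so step 2 is met and the log should be disregarded.
2. 85 − 80 = 5 < 10, so step 3 is also met and the log goes to review.
3. 135 < 140 and 80 < 90, so item 5d is met and the visit ends without action, although the nurse's systolic reading is 10 mmHg above the 140 limit.

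The error can also run the other way. With a nurse reading of 130/80 and a device reading and log average of 145/85, the differences are again 15/5. Validation under step 3 leads to item 5c, which starts the hypertension protocol in a patient whose nurse reading is at goal.

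**The case against.** The strongest reply is that the order of the steps settles the matter. Step 2 comes first, discards the log and requires an entry that the device is inconsistent. Step 3 then has no log to pass on, and few nurses would chart two contradictory entries. This is a fair account of usual practice and is why the point is minor. It does not remove the defect: step 3 has no 'otherwise', and no text gives step 2 precedence.

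A second reply is that an above-goal nurse reading can be overridden by an at-goal log even with a sound device. For example, nurse 148/85 and device and log 139/80 differ by 9/5. That is true and is how the algorithm is built. But that device is within tolerance on both components, whereas the 15/5 device is one that step 2 says not to trust.

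Third, the repeated parenthesis may only name the differences to compare, and the AND rules cited have separate limits for each component. This supports a copying slip over a deliberate choice, and the correction is the same.

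Fourth, the 10/10 gap is ordinary boundary looseness. A nurse systolic reading of exactly 140, for instance, meets neither item 2 nor item 3 on its own. That stands, and the gap would not merit comment by itself.

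There are also safeguards. The nurse's reading is charted ("Measure and record blood pressure according to JNC 8 standards"). Section 7.3 says of data captured at patient contacts: "Information will be then directed to primary care teams per study protocol". Section 6.5 makes use of the hypertension protocol optional. Treatment stays with the provider: "medication and dose will ultimately be selected and ordered by provider". This last safeguard protects against overtreatment, but it does little in the no-action branch, where no medication order is raised.

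**Conclusion.** The rule is wrong as written, at minor severity. The defect is confined to differences with one component above 10 mmHg and the other below 10 (both rules met) and to exactly 10/10 (neither met). Its frequency cannot be quantified, because the documents give neither device-error rates nor the use of this step across the four health systems. The practical effect is probably small, since a nurse working in order would usually stop at step 2. Home-monitor validation is part of a care algorithm, and no effect on 12-month unplanned hospitalization, power or the analysis is shown. The conclusion rests on a literal reading of steps 2 and 3 and on the absence of any stated precedence between them.

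**What to change.** Reword the condition in step 3 to: *If difference is ≤ 10 mmHg for both systolic AND diastolic*. Leave step 2 unchanged. Replacing only 'or' with 'AND' is not enough, because 10/5 and 5/10, which are validated now, would then join 10/10 under neither rule. Placing exactly 10 on the validated side follows from step 2, which rejects only above 10.

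The cost is one wording edit in Appendix I and in any SmartSet text copied from it. Design, data collection and sample size are unaffected.
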